8.2 Clinical Characteristics

The following continuous variables will be summarized using descriptive statistics by treatment group:

- Duration from onset of illness to study drug administration (hours): [Start date/time of study drug administration] – [Date/time of onset of illness]
- Influenza symptoms score at screening: Average scores of respiratory, constitutional, systemic and total symptoms
- Body temperature (°C) at screening

The following categorical variables will be summarized in contingency tables:

- Influenza subtype (Influenza A/H1, Influenza A/H3, Influenza A/H1 and H3, Unknown, NA)
- Influenza confirmed (by cell culture, qPCR, both, no)
- Rapid kit test results (positive, negative)

When influenza A virus load from qPCR has quantitative value or less than Lower Limit of Quantification (LLOQ), then influenza is confirmed. However, when influenza A virus load from cell culture has only quantitative value, then influenza is confirmed by cell culture.

Summary tables will be presented for ITT, ITTI, and PK populations. Also data will be listed for the ITT population.

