- Constitutional symptoms: headache, feeling feverish, body aches and pains, and fatigue
- Systemic symptoms: headache, feeling feverish, body aches and pains, fatigue, neck pain, interrupted sleep, and loss of appetite
- Total score: all items in Domain 1

Descriptive statistics of actual value and change from baseline for average score in each scale will be presented by treatment group at each visit.

If there are missing values in items in Domain 1, missing data will be handled according to section 10.3.

- Descriptive analysis for AUC of average symptom score from date of baseline assessment to last measurable value of subjects who have at least one post-baseline result.

If there are missing values in average symptom scores between observed ones, the missing values are assumed to fall linearly between observed values.

- Mean daily symptom score on the Domain 1 of the Flu-iiQ™

Average of total symptom score for each time point will be plotted with the SD of mean score.

- Incidence of symptoms on the Domain 1 with Grade 2 or Higher

The proportion of subjects who developed any of the 7 individual influenza symptoms (cough, sore throat, nasal congestion, headache, feeling feverish, body aches and pains, and fatigue from Flu-iiQ™ Domain 1) with moderately or severe in intensity (Grade 2 or higher) will be calculated from baseline to Day 8. Most severe score will be counted per each day. Subjects with incomplete data and no recorded symptoms will not be counted (i.e. did not experience symptoms Grade 2 or higher).

All item scores of Flu-iiQ™ will be listed by each domain and time point. Additional listing for Flu-iiQ™ will be provided including average score of Domain 1 (respiratory, constitutional, systemic, total symptom score), Domain 3, Domain 4 and AUC of Domain 1.

- Viral shedding in nasopharyngeal swab samples

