Viral shedding (titers) of swab samples based on qPCR and cell culture will be evaluated at the scheduled collection times. The listing will include titer results, whether the influenza A is confirmed and Area under the Curve (AUC) of viral loads. However, since cell culture results have information of both influenza A and B, the listing and tables for cell culture will present analysis results regardless of influenza type. Changes in viral shedding will be assessed as the change from baseline in \log_{10} vp/mL and \log_{10} TCID₅₀/mL for qPCR and cell culture respectively. If viral loads are lower than LLoQ (2.18 for qPCR), they will be treated as value without inequality sign. Whereas viral load lower than LLoQ for cell culture (0.75) will be considered as negative value and a negative value will be treated as 0. If the subtype of influenza A is "H1", "NA" or "Unknown", the virus titer from HA assay will be used for cell culture analysis. Otherwise, if the subtype is "H3", the virus titer from NP ELISA will be used.

These will be summarized for each treatment group and collection time.

The following analyses will also be performed:

- Summary of viral shedding results; percentage of subjects with positive/negative viral shedding at each visit (baseline, day 2, 3, 5, 8)
- Duration (in days) of viral shedding; from date/time of baseline assessment to last positive sample. Subjects with at least one positive sample after baseline will be included in the summary.

Statistical Analysis Plan

- AUC of viral levels; from date of baseline assessment to last measurable value of subjects who have at least one post-baseline result (including BLQ (Below the Limit of Quantification) and negative values). If there are BLQ or missing values between measurable values, they are assumed to fall linearly between measurable values.
- Change from baseline in descriptive statistics of viral shedding of Swab Samples; descriptive statistics of actual value and change from baseline for viral shedding of swab samples will be presented by treatment group at each visit.
- Mean viral load titer (log values)
Mean viral load titer for each scheduled time point will be plotted with the SD of mean value.

- Incidence of secondary complications of influenza

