11.1 Pharmacokinetic Analysis

11.1.1 Serum Concentration

Blood samples will be collected from each subject during this study for the determination of the PK of CT-P27 components (CT-P22 and CT-P23) administered as 45 mg/kg and 90 mg/kg. Blood samples for PK analysis will be drawn according to the following schedule.

Day of study period	Time point	Window
Day 1	Pre-infusion	Within 15 minutes prior to the beginning of the infusion
	End of infusion	+15 minutes
	1 hour after EOI	± 15 minutes
Day 2	24 hours after SOI	
Day 3	48 hours after SOI	± 4 hours
Day 8	168 hours after SOI	
Day 15	336 hours after SOI	± 2 days
Day 29	672 hours after SOI	
Day 57	1344 hours after SOI	± 5 days
Day 110 or EOS visit	2616 hours after SOI or EOS visit	

Abbreviations: EOI, end of infusion; SOI, start of infusion; EOS, end of study

Serum samples will be analyzed to determine the concentrations of CT-P27 components (CT-P22 and CT-P23) using a validated immunoassay.

Serum concentrations of CT-P27 components (CT-P22 and CT-P23) will be summarized for PK population by treatment group at each scheduled collection time using descriptive statistics; n, mean, SD, geometric mean, CV%, minimum, median, and maximum values. Mean serum concentration-time profiles of study drug will be plotted by treatment on linear and semi-logarithmic scales based on scheduled sample times. Individual concentrations, scheduled timepoints/actual sample collection times and deviations from scheduled collection times will be presented in data listing by treatment in PK population. Individual linear and semi-logarithmic concentration-time plots (based on scheduled sample times) with respective treatments will also be presented together. Since the placebo group has BLQ values for serum concentration, it will not be

Statistical Analysis Plan

summarized in tables and figures.

The BLQ values prior to the study drug administration will be treated as zero (0). For the BLQ values after study drug administration, the following rules will be applied;

- The BLQ values at the beginning of a subject profile (i.e. before the first incidence of a measurable concentration) will be assigned to zero (0).
- The BLQ values at the end of a subject profile (i.e. after the last incidence of a measurable concentration) will be set to missing.
- Single or 2 consecutive BLQs which fall between two measurable concentrations will be set to missing.
- Two or more consecutive BLQs in terminal phase will be set to zero.

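### The viral-load AUC rule interpolates over observed below-limit qPCR swabs that the same SAP section values at 2.18, which can only raise the AUC of the subjects affected

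*SAP*

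**What the plan says.** All the relevant text on viral titers is in SAP 10.2, under viral shedding.

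- **qPCR below the limit:** "If viral loads are lower than LLoQ (2.18 for qPCR), they will be treated as value without inequality sign". Such a swab is therefore worth 2.18 log10 vp/mL.
- **Cell culture below the limit:** "viral load lower than LLoQ for cell culture (0.75) will be considered as negative value and a negative value will be treated as 0".
- **AUC window and inclusion:** the AUC runs "from date of baseline assessment to last measurable value of subjects who have at least one post-baseline result". A bracket after these words says that BLQ and negative swabs both count as results for this purpose.
- **AUC gap rule:** "If there are BLQ or missing values between measurable values, they are assumed to fall linearly between measurable values".

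Three other places bear on the reading.

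- SAP 8.2 accepts a below-limit qPCR result as evidence of infection: "When influenza A virus load from qPCR has quantitative value or less than Lower Limit of Quantification (LLOQ), then influenza is confirmed".
- The symptom-score AUC in SAP 10.2 interpolates only what was not observed: "If there are missing values in average symptom scores between observed ones, the missing values are assumed to fall linearly between observed values".
- The serum concentration rules in SAP 11.1.1 do discard some embedded below-limit results: "Single or 2 consecutive BLQs which fall between two measurable concentrations will be set to missing".

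Protocol 8.5.2 plans changes in viral shedding but no viral AUC. SAP 13 lists no change or reason for the viral AUC rule; its BLQ item concerns PK.

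**The concern.** A below-limit qPCR swab carries information: the titer is under 2.18. The section uses that information when it assigns a value and when it decides who enters the AUC, then drops it when the area is computed. The same swab is 2.18 in the by-visit means and changes from baseline, but may be 4 log10 or more in the AUC.

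The AUC is meant to summarise how much virus a subject shed over the sampling period. If a swab that shows a fall below the limit is replaced by a value on the line between its neighbours, the fall disappears from that subject's summary. AUC tables are planned for qPCR and culture in both the ITT and ITTI populations (SAP 14.7, Tables 14.2.12.1.1 to 14.2.12.2.2), and Protocol 6.5 names quantitative change in viral shedding as the primary virology outcome.

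**Working it through.** The documents give no AUC figure to reproduce, so the check compares the two rules on the same profiles.

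**Inputs**
- Swab times 0, 1, 2, 4 and 7 days, for baseline and Days 2, 3, 5 and 8 (schedules in Protocol Table 1 and SAP 14.1). Placing baseline at time 0 is an assumption.
- Below-limit values 2.18 (qPCR) and 0 (culture), from SAP 10.2.
- Linear trapezoids on the log10 scale, ending at the last measurable value. The trapezoid and the scale are assumptions; SAP 10.2 states log10 units for the changes from baseline.
- All titers are invented for illustration. B means below the limit.

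**Direction.** If both neighbours are at or above 2.18, every point on the line between them is at or above 2.18. For one embedded B, the AUC changes by

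(interpolated value − assigned value) × (time between the two neighbouring swabs) ÷ 2,

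which cannot be negative.

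**qPCR 6, 5, B, 2.5 at days 0, 1, 2, 4**
- SAP rule: (6+5)/2×1 + (5+2.5)/2×3 = 5.5 + 11.25 = 16.75. The value inserted at day 2 is 5 − 2.5/3 = 4.17.
- Section's own value: 5.5 + (5+2.18)/2×1 + (2.18+2.5)/2×2 = 5.5 + 3.59 + 4.68 = 13.77.
- Difference 2.98, or +22%. The formula agrees: (4.167 − 2.18) × 3/2 = 2.98.

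**Near the limit: qPCR 2.3, 2.2, B, 2.2 at days 0, 1, 2, 4**
- 8.85 against 8.82, a difference of (2.2 − 2.18) × 3/2 = 0.03, or +0.3%.

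**Ranking over days 0, 1, 2, 4, 7**

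| qPCR profile | SAP rule | Own values, to last measurable | Own values, to day 7 |
|---|---|---|---|
| 6, 5, 4, 3, 2.5 | 25.25 | 25.25 | 25.25 |
| 6, 5, B, B, 2.5 | 28.00 | 20.47 | 20.47 |
| 6, 5, B, B, B | 5.50 | 5.50 | 19.99 |

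- Row 2, SAP rule: 5.5 + (5+2.5)/2×6 = 28.00. Own values: 5.5 + 3.59 + 2.18×2 + (2.18+2.5)/2×3 = 20.47.
- Row 3 to day 7: 5.5 + 3.59 + 2.18×2 + 2.18×3 = 19.99.

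Under the SAP rule the subject in row 2, who fell below the limit twice, scores above the subject in row 1, who never did. Rows 2 and 3 differ only in the last swab (2.5 against below 2.18), yet the SAP gives 28.00 and 5.50.

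**Cell culture, only if the gap rule is read to include negatives: 4, 3, negative, 1 at days 0, 1, 2, 4**
- Interpolated: 3.5 + (3+1)/2×3 = 9.5. With the section's 0: 3.5 + 1.5 + 1.0 = 6.0. That is +58%.

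**qPCR negative between measurable values.** The gap rule names BLQ and missing, not negative, and the value 0 appears in the sentence on culture. For 6, 5, x, 4 at days 0, 1, 2, 4 the AUC is 19.00 if x is interpolated, 15.27 if x = 2.18 and 12.00 if x = 0.

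**The case against.** **It may be a deliberate convention.** The PK rules in the same SAP also set aside embedded below-limit results. But that rule is limited to one or two consecutive results, whereas the viral rule has no limit. Nothing in SAP 10.2 adopts the PK convention or reconciles it with the values 2.18 and 0. The symptom-score AUC in the same section does not follow it.

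**Culture may not be affected.** The inclusion bracket names BLQ and negative separately, and the gap rule then names only BLQ and missing. Since a culture result under 0.75 is defined as negative, it may lie outside the gap rule. This is a fair reading, so the culture figures above are conditional. What stands for culture is that the text should say so.

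**Stronger readings go too far.** A reader might infer that the viral AUC is always too large. The table shows otherwise: ending at the last measurable value gives a subject who clears and stays clear 5.50 instead of 19.99, a larger shift in the other direction. A reader might also infer that the rule hides an antiviral effect, because embedded below-limit swabs should be commoner in the arm that clears faster. Neither document gives their frequency by arm, and the pattern needs a later return to measurable virus, which need not favour either arm. Nor do the documents make viral AUC the main readout for dose selection. SAP 1.1 bases that on effect size in time to resolution, with safety and PK; Protocol 2.2 adds efficacy only in general terms.

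**Little may change in practice.** Near the limit the difference is trivial. The by-visit values, percentages positive and mean plots do not depend on the gap rule. This stands, and it limits the importance of the point.

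**Conclusion.** The point holds for qPCR. SAP 10.2 gives an observed below-limit swab two different values, and the one used in the AUC contradicts the assay result or, at the least, never sits below the limit. For an affected subject the rule can only raise the AUC. In the examples the rise runs from 0.3% near the limit to 37% (28.00 against 20.47), and the order of subjects can reverse. These sizes rest on invented titers, nominal swab times and log-scale trapezoids; the direction does not depend on the titers chosen.

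For culture the same conflict arises only under one reading of the sentence. The net effect on any comparison between arms is unknown in both size and sign, because the frequency of embedded below-limit swabs is not given and the end-of-window rule pulls the other way. The AUC is a descriptive summary within a secondary endpoint, and the primary analysis is untouched. The correction is worth making because the rule is wrong where it acts and costs almost nothing to change.

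**What to change.** Revise the AUC bullet in SAP 10.2 to say four things:

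1. Linear interpolation applies only to swabs that were not taken or gave no result.
2. Observed below-limit swabs enter the AUC at the values the section already assigns: 2.18 for qPCR below the limit, and 0 for a culture that is below 0.75 or negative.
3. The value given to a qPCR negative is stated, and is the same in the AUC and the by-visit summaries.
4. The AUC runs to a common end, Day 8 or the last swab taken, so that trailing below-limit swabs also count at their assigned values. If the last swab taken is used, report how many subjects have a shorter window.

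Items 1 and 4 belong together. Changing only the gap rule would leave the three qPCR profiles in the table at 25.25, 20.47 and 5.50; with both changes they are 25.25, 20.47 and 19.99.

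The cost is a few sentences in the SAP and a small programming change, with no new data and no new tables. If the SAP is already final, SAP 5.1 provides for recording and justifying the departure in the study report.

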6.5 Appropriateness of Measurements

The primary and secondary efficacy endpoints are consistent with the "Guidance for Industry: Influenza: Developing Drugs for Treatment and/or Prophylaxis" provided by the FDA. The Flu-iiQ™ used in this study is a validated questionnaire developed to evaluate the influenza symptoms.

The primary virology outcome, quantitative changes in viral shedding, is assessed using standard qPCR and cell culture methods.

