8.5.2 Secondary Efficacy Analyses

The secondary efficacy endpoints will be analyzed on the ITTI and ITT populations.

Time (in days) to resumption of normal activity, return to normal body temperature ($<37.0^{\circ}\text{C}$), and resolution of individual symptoms will be analyzed using a Kaplan Meier model to assess differences between placebo and CT-P27.

Individual symptoms and total symptom score will be summarized by severity, by time point, and by treatment group.

Viral shedding (titers) based on qPCR and cell culture will be evaluated at the scheduled collection times. Changes in viral shedding will be assessed as the change from baseline in qPCR and \log_{10} TCID₅₀/mL.

These will be summarized for each treatment group and collection time.

The number and percentage of subjects with secondary complications of influenza will be summarized by treatment group.

Results for questions included in the remaining domains (3 and 4) (effect on feelings, effect on concerns) of the Flu-iiQ™ will be summarized by collection time and treatment group.

Scheduled selection times are presented in [Table 1](#).

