14.2.11.2.1	ITT	Descriptive Statistics of Duration of Viral Sheddings from Cell Culture	Listing 16.2.6.3.2 Virus Titer Results from Cell Culture
14.2.11.2.2	ITTI	Descriptive Statistics of Duration of Viral Sheddings from Cell Culture	Listing 16.2.6.3.2 Virus Titer Results from Cell Culture
14.2.12.1.1	ITT	Descriptive Statistics of AUC of Viral Loads from qPCR	Listing 16.2.6.3.1 Virus Titer Results from qPCR
14.2.12.1.2	ITTI	Descriptive Statistics of AUC of Viral Loads from qPCR	Listing 16.2.6.3.1 Virus Titer Results from qPCR
14.2.12.2.1	ITT	Descriptive Statistics of AUC of Viral Loads from Cell Culture	Listing 16.2.6.3.2 Virus Titer Results from Cell Culture
14.2.12.2.2	ITTI	Descriptive Statistics of AUC of Viral Loads from Cell Culture	Listing 16.2.6.3.2 Virus Titer Results from Cell Culture
14.2.13.1.1	ITT	Change from Baseline in Descriptive Statistics of Viral Sheddings of Swab Samples from qPCR	Listing 16.2.6.3.1 Virus Titer Results from qPCR
14.2.13.1.2	ITTI	Change from Baseline in Descriptive Statistics of Viral Sheddings of Swab Samples from qPCR	Listing 16.2.6.3.1 Virus Titer Results from qPCR
14.2.13.2.1	ITT	Change from Baseline in Descriptive Statistics of Viral Sheddings of Swab Samples from Cell Culture	Listing 16.2.6.3.2 Virus Titer Results from Cell Culture
14.2.13.2.2	ITTI	Change from Baseline in Descriptive Statistics of Viral Sheddings of Swab Samples from Cell Culture	Listing 16.2.6.3.2 Virus Titer Results from Cell Culture
14.2.14.1	ITT	Summary of Presence of Secondary Complications of Influenza A	Listing 16.2.6.4 Secondary Complications of Influenza A
14.2.14.2	ITTI	Summary of Presence of Secondary Complications of Influenza A	Listing 16.2.6.4 Secondary Complications of Influenza A
14.2.15.1	ITT	Use of Antibiotics for Subjects with Secondary Complications	Listing 16.2.4.8.1 Prior and Concomitant Medications, Listing 16.2.6.4 Secondary Complication of Influenza A

CONFIDENTIAL

54/62 page

Effective Date: 01-Aug-2018

Statistical Analysis Plan

14.2.15.2	ITTI	Use of Antibiotics for Subjects with Secondary Complications	Listing 16.2.4.8.1 Prior and Concomitant Medications, Listing 16.2.6.4 Secondary Complication of Influenza A
14.2.16.1	ITT	Change from Baseline in Descriptive Statistics of Effect on Feelings (Flu-iiQ Domain 3) - Total	Listing 16.2.6.1.1 Flu-iiQ: Average Score and AUC

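### Viral load, which Protocol 6.5 calls the primary virology outcome, has no planned dose-minus-placebo estimate, confidence interval or baseline adjustment

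*SAP*

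**What the plan says.** Protocol 6.5 states: "The primary virology outcome, quantitative changes in viral shedding, is assessed using standard qPCR and cell culture methods". The endpoint lists (Protocol 8.2.2, SAP 3.1) place viral shedding among the secondary efficacy endpoints, with no stated priority.

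Protocol 8.5.2 says of the titers and their changes: "These will be summarized for each treatment group and collection time". SAP 10.2 sets the scale: "Changes in viral shedding will be assessed as the change from baseline in" log10 vp/mL for qPCR and log10 TCID50/mL for cell culture. It then lists the outputs:

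- actual value and change: "descriptive statistics of actual value and change from baseline for viral shedding of swab samples will be presented by treatment group at each visit"
- positivity: "percentage of subjects with positive/negative viral shedding at each visit"
- duration: "from date/time of baseline assessment to last positive sample"
- AUC: "AUC of viral levels; from date of baseline assessment to last measurable value of subjects who have at least one post-baseline result"
- plots of mean titer with SD.

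The viral tables in SAP 14.7 match this. A typical title is "Change from Baseline in Descriptive Statistics of Viral Sheddings of Swab Samples from qPCR". No table there holds a between-arm difference or a model result for viral load. By contrast, the time-to-event secondary endpoints in the same SAP section carry a stated aim of assessing differences between placebo and CT-P27.

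**The concern.** The sample size sections (Protocol 8.1, SAP 5.2) say the study is designed to obtain effect sizes, and Protocol 2.2 cites earlier trends in viral shedding as part of the rationale. Titer is the most direct measure of antiviral activity collected, yet no effect size for it is specified. A reader would have to compare arm-level summaries by eye, or choose a contrast after seeing the data.

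The baseline titer, measured before dosing, is left unused as a covariate. Raw change subtracts the whole baseline value, and the raw visit value subtracts none of it. Neither is in general the right weight. Randomization is stratified by vaccination history and PK sub-study participation, so nothing in the design balances baseline titer or influenza subtype.

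For culture there is a further wrinkle. A subject enters the ITTI population on a positive qPCR or culture result, and a negative culture is scored 0. A subject who is culture-negative at baseline therefore cannot show a fall. The culture titer also comes from different readouts by subtype (HA assay or NP ELISA).

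**Working it through.** **Inputs.** Planned evaluable subjects are 63 per CT-P27 arm and 38 on placebo (SAP 5.2). The only design calculation in the documents is for the primary endpoint: 80% power for 1.8 days with SD 3 days. It reproduces (81.4% with the Wilcoxon efficiency factor 3/π, 80.4% by simulation), but it says nothing about viral load. There is no plan figure for viral load to reproduce. The correlation and SD ratio below are assumptions.

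**Formulas.** Set the baseline SD to 1, the visit SD to k, and the baseline-to-visit correlation to ρ. Up to a common factor in the arm sizes, the large-sample variance of the arm difference is:

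- raw change: 1 + k² − 2ρk
- raw visit value: k²
- baseline-adjusted (ANCOVA): k²(1 − ρ²)

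**Direction.** Raw change minus ANCOVA is 1 − 2ρk + ρ²k² = (1 − ρk)², which is never negative. Raw visit value minus ANCOVA is ρ²k², also never negative. The direction needs no assumption about ρ or k.

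**Size against raw change, equal SDs (k = 1).** The reduction is 1 − (1 − ρ²)/[2(1 − ρ)] = (1 − ρ)/2.

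| ρ | raw change | ANCOVA | variance reduction | SE reduction |
|---|---|---|---|---|
| 0.1 | 1.80 | 0.99 | 45% | 26% |
| 0.3 | 1.40 | 0.91 | 35% | 19% |
| 0.5 | 1.00 | 0.75 | 25% | 13% |
| 0.7 | 0.60 | 0.51 | 15% | 8% |
| 0.9 | 0.20 | 0.19 | 5% | 2.5% |

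**Size against raw change, unequal SDs.**

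| k | ρ = 0.3 | ρ = 0.5 |
|---|---|---|
| 0.75 | 54% | 48% |
| 1.25 | 22% | 11% |
| 1.5 | 13% | 4% |

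The extremes, worked out:

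- k = 0.75, ρ = 0.3: 1 − 0.5625 × 0.91/1.1125 = 54%
- k = 1.5, ρ = 0.5: 1 − 2.25 × 0.75/1.75 = 4%

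**Size against the raw visit value.** The reduction is ρ², which is 9% at ρ = 0.3 and 25% at ρ = 0.5, whatever k is. Against the better of the two tabulated summaries, the gain over ρ = 0.3 to 0.5 and k = 0.75 to 1.5 runs from about 4% to 25%.

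**Baseline imbalance.** The SE of the baseline difference is √(1/63 + 1/38) = 0.205 SD. The 95% limit is 1.96 × 0.205 = 0.40 SD, and the median absolute imbalance is 0.674 × 0.205 = 0.14 SD. This is one source of the variance already counted above, not an extra loss.

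**The case against.** The strongest reply is that nothing is lost, because nothing is tested. Viral shedding is a secondary endpoint, and the protocol and SAP agree on describing it. SAP 5.1 requires n, mean and SD for continuous variables, so a crude difference with a CI can be computed from the planned tables. The wording in Protocol 6.5 is one phrase in a section on the suitability of measurements. For dose selection, SAP 1.1 names the effect size on time to resolution, safety and PK; Protocol 2.2 adds only efficacy in general. Neither names viral load. Much of this stands. It shows that the gap is one of prespecification and efficiency, and that the information is not absent.

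Four stronger readings are tempting, and the documents do not support them:

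- *Raw change is the only summary.* The sentence quoted from SAP 10.2 also covers actual values, and positivity, duration and AUC are listed beside it.
- *The plan discards 25–35% of its precision.* That needs ρ of 0.3 to 0.5 and equal SDs, neither of which the documents give. Sub-LLoQ qPCR values are held at 2.18 and culture values below 0.75 become 0, so SD and correlation may differ by visit. One figure for all visits is not supportable.
- *A serious baseline imbalance is likely.* 0.40 SD is the 95% limit; 0.14 SD is the median.
- *Culture-negative subjects dilute the culture change by a known amount.* No document gives their number, and their cultures could turn positive later. Percent positive at baseline is already tabulated by arm.

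What survives is that no contrast is fixed in advance, and that the collected baseline titer is not used to sharpen one.

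**Conclusion.** The point holds in a limited form. For the outcome that Protocol 6.5 calls primary in virology, neither document plans a dose-minus-placebo estimate, a confidence interval or a baseline adjustment. In large samples a baseline-adjusted difference is at least as precise as either unadjusted comparison that a reader could make from the tables, for any correlation and SD ratio.

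The size rests on assumptions. Against raw change with equal SDs, the variance reduction is 35% to 25% for ρ of 0.3 to 0.5 (19% to 13% on the SE scale), and 45% to 5% for ρ of 0.1 to 0.9. With SD ratios of 0.75 to 1.5 and ρ of 0.3 to 0.5, it is about 54% to 4%. Against the raw visit value it is 9% to 25% for ρ of 0.3 to 0.5. The primary efficacy analysis and its power are not affected.

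**What to change.** In SAP 10.2, keep all the descriptive viral outputs and add the following.

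- **Model.** For log10 qPCR and log10 TCID50/mL in the ITTI population, fit a linear model of the visit value on treatment, with baseline titer and influenza subtype as covariates. Put Unknown, NA and mixed H1/H3 into a subtype category of their own so that no subject drops out.
- **Output.** Report each dose-minus-placebo adjusted difference with a 95% CI at Days 2, 3, 5 and 8. Name one key visit before unblinding, and label the remaining contrasts as estimates without multiplicity control.
- **Supportive analysis.** Repeat the model in subjects positive at baseline on the assay in question. The restriction uses a pre-dose result, so the randomized comparison is kept.
- **Caveat.** State that values at the floor (2.18 for qPCR, 0 for culture) may accumulate at later visits and limit what a linear model can say there.
- **Record.** Add the analysis to SAP section 13 and the table list in 14.7.

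The cost is one SAP paragraph and one table per assay, from data already collected.
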